7.1.2 Selection of Trial Method and Justification

The nature of this clinical study is medical device registration clinical validation. Therefore, it is necessary to comply with the relevant regulations such as the "Provisions for Medical Device Registration" and the "Quality Management Practice for Clinical Trials of Medical Devices" promulgated by the CFDA.

7.1.2.1 Reason for selection of the control group

After searching the China Food and Drug Administration (CFDA) medical device database, St. Jude Medical's Pressure Guidewire and Analyzer Express are listed as CFDA approved products. The selection of the control device for this trial is based on the following:

- (1) The basic principle and the indication for use of the control device are the same as those of the investigational device;
- (2) The control device has been on the market in China and has a wide clinical use, with good clinical effectiveness and safety.

7.1.2.2 Reasons for the selection of the trial population

According to the investigational device's indication for use, the trial population selected in this clinical trial is to perform coronary angiography to determine the

degree of stenosis. Such trial population satisfies the relevant range of indication for use and is representative.

7.1.2.3 Reason for the selection of the endpoints

The primary effectiveness endpoint is the diagnostic consistency of FFR_{WS}, for diagnosis of coronary heart disease measured by Zurich Medical's Pressure Guidewire System.

7.1.3 Measures to Lessen and Prevent Bias

This clinical trial will use the following methods to lessen bias in trials.

Multi-center: Case samples from multiple centers are more representative than single centers, preventing systemic errors in a single center from biasing the trial results, and obtained conclusions are more credible. To reduce the operational differences between the investigational sites, investigators should be trained by uniform standard, and clear evaluation criteria should be adopted for the effectiveness indicators and safety indicators.

Control: This study is a single-subject design clinical trial. Subjects use investigational device then control device to complete FFR measurements, preventing factors that may affect efficacy judgment.

Investigator Training: Before the clinical trial begins, the auditor and the head of investigational site will provide training for investigators, so investigators will gain understanding and become familiar with the investigational device. Investigators should also have grasp on all new findings during the clinical trial that's related to the investigational device.

Clinical Trial Monitoring: Develop inspection plan. Sponsor appoints auditors to conduct regular on-site audit of investigational sites, ensure that all content of the research program is strictly observed, and the original data is checked for consistency with the contents on the EDC.

7.1.4 Investigational Medical Devices and Controlled Medical Devices /

[figure not shown]
Control Methods

The ICA examination performed by qualified interventional cardiologist. After the informed consent form is signed, coronary angiography will be taken from different positions via standard operating procedures. After enrollment, and registration in the central registration system, investigator will first use investigational device to perform FFR measurement, then use control device to remeasure FFR of the same vessel. The interval between two measurements should be greater than 3 minutes. The pressure guidewire

and catheter should be flushed with saline. Nitroglycerin to be used to eliminate coronary artery spasm, and ATP are to be infused through the central vein (intermediate elbow or femoral vein) at 140-180 $\mu\text{gkg}^{-1}\text{min}^{-1}$ to place the coronary vessels in hyperemia state. FFR measurements should be performed by qualified, experienced, and trained physicians, primarily focus on stenosis that shows moderately stenotic lesions (diameter stenosis 30% - 70%) in vessels that's ≥ 2.5 mm in diameter. The FFR results from the investigational device and the control device are not be used as a reference basis for further stent therapy. See operational instruction below:

DIRECTIONS TO USE ZURICH PRESSURE GUIDEWIRE SYSTEM 1-SENSOR METHOD TO TAKE MEASUREMENTS:

- 1) Open the package using sterile techniques
- 2) Fill the coil with saline solution, using the flush port
- 3) Soak Guidewire in saline until calibration is complete
- 4) Gently detach the portable display unit from the tray
- 5) Carefully wipe and dry the proximal end of Guidewire and insert into Handle (see Figure 1 for proximal end location of Guidewire)
- 6) Open the portable display unit by lifting the screen. This turns on the portable display unit

[figure not shown]

- 7) Verify the Guidewire-handle connection status icon is  displayed in the upper left corner to confirm the correct connection

- 8) Ensure the tray containing the Guidewire is at the same height as the patient's heart
- 9) Press the button  once for calibrating the system to zero atmospheric pressure (the

button is on the back of the screen). **CAL** will be displayed in the action state box at bottom center of the display

- 10) Carefully remove the Guidewire from the package coil

WARNING: Guidewire is a delicate instrument and should be handled carefully. Bending or excessive force during removal from packaging tray may damage the guidewire.

CAUTION: If recalibration is necessary during the case, remove Guidewire from the body and follow the RESET procedure after step 20.

NOTE: After calibration, the Guidewire may be disconnected from the Portable Display for ease of advancement.

- 11) Engage the guiding catheter using standard practice and flush the catheter with sterile saline solution

WARNING: When introducing the Guidewire, confirm that the catheter tip is free within the vessel lumen and is not touching the vessel wall. Failure to do so may result in vessel trauma upon Guidewire exit of the catheter. Use the radiopaque marker of the catheter to confirm position.

- 12) Carefully insert the distal tip of the guidewire into the hemostatic valve of the Y connector. Advance Guidewire out of the guiding catheter and steer Guidewire to a location just proximal to the lesion of interest

- 13) Pull back the insertion tool out of the hemostatic valve and tighten the hemostatic valve

- 14) If the Guidewire has been detached from the Portable Display, carefully wipe and dry the proximal end and reconnect it now with the Handle. Verify the connection by checking for  in the upper left corner of the display

- 15) If estimating FFR, induce maximum hyperemia using standard clinical practice

CAUTION: Failure to achieve maximum coronary and myocardial hyperemia may result in invalid FFR.

- 16) Save the pressure proximal to the lesion of interest by pressing and holding the **BUTTON**

 until **SAV** is displayed in the action status box. At this point **RELEASE** the **BUTTON** 

- 17) Advance Guidewire across the lesion and perform pressure measurement

WARNING: Observe all Guidewire movements. Whenever Guidewire is moved or torqued, the tip movement should be examined under fluoroscopy.

WARNING: Torque Guidewire against resistance or repeated attempts to cross a total vessel occlusion may cause damage and/or fracture, which may lead to a portion of Guidewire separating from the tip.

CAUTION: Do not measure pressure when the sensor element of Guidewire is in sharp curves, since this might result in pressure artifacts.

NOTE: When a position of interest is difficult to reach, Guidewire may be disconnected from the Portable Display for easier use. Carefully wipe and then dry the male connector before reconnecting to Handle.

[figure not shown]

[figure not shown]

Diagram 3: Live Data Screen 1-Sensor Method

- 18) Double-click the BUTTON  to begin recording an episode. **REC** will display in the action status box;
- 19) Press the  BUTTON again to once to end recording an episode. The data review screen of the episode will appear on the display. The two lowest FFR values will be displayed

[figure not shown]
20) Press the BUTTON  again once to return to live data screen;

WARNING: Excessive manipulation when sensor element or tip of Guidewire is located in sharp bend may cause damage or tip fracture. If the guiding catheter is in an anatomically severe or sharp bend, for example a tortuous subclavian artery or adjacent vessel position, the junction between the shaft and the flexible distal section of the wire, 31 cm from the tip, may be vulnerable to kinking or fracture.

DIRECTIONS TO RESET

NOTE: If for any reason, the Portable Display needs to be reset and returned to out-of-the-box settings, do the following

1. Press and hold the BUTTON  for more than 5 seconds until the RESET screen appears

2. Press the BUTTON  again to confirm reset to out of the box settings
3. If an inadvertent BUTTON  press for more than 5 seconds occurs, wait until the countdown clock reaches 0 and the portable display will return to the screen before the reset mode is activated

WARNING: Recalibration is required following RESET. Remove Guidewire from the body and follow the instructions above to calibrate.

Use St. Jude Medical 's Fractional Flow Reserve (FFR) Measuring Device to Measure FFR:

- 1) Connect the power cord, connect the aortic pressure input cable, and turn on the Analyzer Express
- 2) Select or create a new patient
- 3) Engage the guiding catheter in accordance with standard procedures and flush the

guiding catheter

- 4) Place the AO sensor at the same height as the patient's heart, connect the pressure sensor to the air (through the atmosphere), and zero the aortic pressure;
- 5) Open the pressure guide wire package and leave the pressure guide wire in the tray
- 6) Fill the packaging coil with heparin saline through the innermost rinse port of the packaging coil
- 7) Connect the pressure guidewire to the Analyzer Express, and zero the pressure guidewire
- 8) Gently remove the pressure guidewire from the packaging coil
- 9) Insert the pressure guidewire into the guiding catheter and advance the pressure guidewire until the pressure sensor just outside of the guiding catheter
- 10) Equalize the Pd and Pa values
- 11) Push the pressure guidewire to the distal end of the lesion and record the vessel and position
- 12) Record the resting Pd/Pa through the pressure guidewire
- 13) Use standard catheter laboratory procedures for administer nitroglycerin, then adenosine from the vein to achieve hyperemia
- 14) Record the FFR value through pressure guidewire
- 15) Retract the pressure guidewire until the sensor just outside of the guiding catheter, the pressure wire position is similar to the position during the equalization of Pa and Pd earlier, and verify that the difference between the aortic mean pressure (Pa) and the pressure guidewire reading of mean pressure (Pd) is within ± 3 mmHg. ;
- 16) Repeat the step 6 – 11 to measure other lesions
- 17) Remove the pressure guidewire from the body

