5.2.2 Working Principle and Functional Mechanism

Fractional Flow Reserve (FFR) based on the principle of anatomy and functional regulation of coronary artery circulation defined as the ratio of the maximum blood flow to the myocardium of the epicardial stenosis coronary artery and the maximum blood flow to the myocardium when the same coronary artery is healthy. It's equivalent to the average pressure of the distal-end of stenosis during a hyperemia state (P_d) and the average aortic pressure during hyperemia state (P_a) (Figure2). Clinically using vessel dilator to induce hyperemia in myocardium, can reduce cardiac microcirculation resistance small enough and become negligible and constant, at this time the myocardial blood flow is only affected by perfusion pressure, so that the reduction of perfusion pressure in the hyperemia state can be equivalent to the degree of narrowness as the heart muscle blood flow is reduced.

FFR: Fractional Flow Reserve

Assess whether stenosis causes myocardial ischemia

The gold standard for clinical assessment whether the stent implantation is necessary

$$FFR = P_d / P_a \text{ (during hyperemia)}$$

$FFR > 0.8$ No interventional treatment required

$0.75 < FFR \leq 0.8$ Doctor's assessment

$FFR \leq 0.75$ Interventional treatment (implant stent)

Figure 2: The basic principles of calculating fractional flow reserve (FFR)

The product can measure FFR using the conventional AO method, as shown in Figure3.

[figure not shown]

Figure 3: AO Method Real-Time Data Screen

In addition to being able to measure FFR using the above conventional AO method, the pressure guidewire system also provides an innovative I-sensor method for FFR measurement, i.e. measuring at different parts of the vessel using the same sensor. Using the same sensor to measure in different parts of the blood vessel, is more accurate and reduce the error that can be generated by using two sensors. FFR value is automatically calculated and displayed by the precise algorithm provided by the portable display unit in real time. The innovative I-sensor measurement as shown in Figure 4:

[figure not shown]

Figure 4: I-Sensor Method Real-Time Data Screen

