6 PRODUCT'S INDICATION FOR USE AND CONTRAINDICATIONS, WARNING

6.1 Indication for use

For patients who need coronary angiographic examination and coronary interventional treatment, pressure guidewire system is indicated to calculate the patient's fractional flow reserve (FFR), and to assist the physicians to make clinical decisions.

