7.1.5 Subject Selection (including control group selection if necessary)

(1) Inclusion Criteria

Patients must meet all the following inclusion criteria to qualify for enrollment:

- 1) Age 18 to 75 years old, gender-unrestricted, non-pregnant female;
- 2) Understand and be willing to sign an informed consent form;
- 3) Diagnosed with coronary heart disease;

- 4) Intrusive ICA and FFR measurement are needed;
- 5) Visual coronary angiography showed at least one moderate stenosis lesion (diameter stenosis of 30% - 70%) on the coronary artery with diameter $\geq 2.5\text{mm}$

(2) Exclusion Criteria

Patients meet any of the following criteria is not qualified for enrollment:

- 1) Patient who do not understand or are unwilling to sign an informed consent form;
- 2) Has a history of myocardial infarction;
- 3) Patient with other serious diseases are not suitable for clinical trials, such as a complex congenital heart disease history, severe heart failure (NYHA cardiac function level IV), long QT syndrome, severe hypertension, Severe asthma, severe chronic obstructive pulmonary disease, liver and kidney dysfunction and other serious infections and critical illnesses;
- 4) Coronary intervention surgery contraindications;
- 5) Patient with ATP contraindications (ATP contraindications: sinus syndrome, sinus insufficiency and the elderly with cautious use or no use);
- 6) The clinical manifestations of patients show acute instability, including acute chest pain (sudden appearance), cardiogenic shock, unstable blood pressure (systolic pressure less than 90mmHg), severe congestive heart failure or acute pulmonary edema;
- 7) The angiography shown or suspect of thrombosis;
- 8) The angiography shown or suspect of dissection;
- 9) Left main coronary artery disease, target blood vessels with severe curvature or calcification lesions, total occlusion;
- 10) There are any other factors that the investigator considers unsuitable for inclusion or completion of this study.

(3) Standards and procedures for terminating trial / trial treatment

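### As written, Section 7.1.4 keeps the approved control wire's FFR, not only the investigational wire's, out of the stent decision, in subjects who must need an FFR to be enrolled

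*Combined protocol and SAP*

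**What the plan says.** The rule stands in Section 7.1.4, in the paragraph on how the two measurements are made: "The FFR results from the investigational device and the control device are not be used as a reference basis for further stent therapy". It names both devices and gives no reason.

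Other sections describe who is enrolled and what the control reading is for:

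- Section 7.1.5, inclusion criterion 4: "Intrusive ICA and FFR measurement are needed".
- Section 7.1.2.1, on the control pressure wire and its analyzer: "Analyzer Express are listed as CFDA approved products", and "The control device has been on the market in China and has a wide clinical use, with good clinical effectiveness and safety".
- Section 7.1.2.1, item 1: "The basic principle and the indication for use of the control device are the same as those of the investigational device". Section 6.1 gives that indication as calculating FFR and "to assist the physicians to make clinical decisions".
- Section 5.2.2, on FFR: "The gold standard for clinical assessment whether the stent implantation is necessary". It then ties ranges to actions. Above 0.80 the entry reads "No interventional treatment required"; above 0.75 and up to 0.80 is left to the doctor; 0.75 or below calls for intervention with a stent.

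**The concern.** Keeping a device under test out of treatment decisions needs no defence. The difficulty is that the same sentence removes the control reading. A subject who needs an FFR has one taken with a marketed wire whose stated purpose is to support clinical decisions, and the physician is told not to use it for the decision in which the protocol gives FFR the leading role.

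What is at stake is the care of subjects. The agreement estimate is not at stake.

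**Working it through.** **1. Does the rule reach the control wire?** Yes. The sentence in 7.1.4 names both devices, and no other section exempts the control reading.

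**2. Does another provision lift it?** Each candidate was read against the sentence.

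- Section 7.1.5 (3) lets the investigator withdraw a subject on medical judgment at any time and preserves access to other standard treatment. This is withdrawal text. It gives a way out of the trial and does not permit use of the control reading within it.
- Section 14.1 allows deviation without the sponsor's written approval in a medical emergency, to protect life or physical health or to avoid significant harm. An elective decision on a moderate stenosis will not usually meet that test.
- Section 20.2, item 12 leaves trial-related medical decisions with the investigator, but item 8 of the same section requires strict adherence to the protocol.
- No separate clinical FFR is provided. Section 8.4 lists use of a third-party product among the reasons for drop-out from the primary analysis.

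So the rule is softened and not removed.

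**3. Is the rule needed for the primary endpoint?** Section 7.1.6.2 defines the consistency rate as (true positive + true negative) / (positive + negative), from FFR values recorded at Visit 2. Treatment given after both values are recorded does not enter the formula. Section 7.1.3 lists four measures against bias (multiple centers, within-subject control, training, monitoring). Neither this rule nor operator blinding is among them.

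**4. How many subjects are in each range?** Inputs: 300 planned subjects (7.1.5 (7)) and a positive-to-negative ratio of about 1:2 at the 0.80 cut-off (8.2.1).

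- Control FFR at or below 0.80: 300 × 1/(1 + 2) = 100
- Control FFR above 0.80: 300 × 2/(1 + 2) = 200

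These reproduce the plan's own figures of about 100 and about 200 in 8.2.1. By the ranges in 5.2.2, about 200 subjects would fall where no intervention is called for, and about 100 where a stent or the doctor's assessment applies. The documents do not divide those 100 at 0.75.

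**5. How many stent decisions would change?** This cannot be derived. It would need the decision each physician would make without FFR, and the plan gives no rule for that. The figures in step 4 count subjects under the rule, not decisions altered.

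**The case against.** The strongest case for leaving the rule alone concerns the reference reading. The investigational wire is always used first, no operator blinding is described, and the control FFR is the reference for the primary endpoint. If that reading may drive treatment, an operator who has already seen the investigational value gains a clinical interest in how the reference comes out. The rule removes that interest. This stands as a real cost of any change, though the plan does not give it as its reason. Recording both readings before either can be used, and fixing which reading is analyzed, limits the cost but does not remove it.

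Three further points have weight.

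- The sentence is garbled in translation and may have been meant only for the investigational wire. A reader might infer a deliberate decision to withhold an approved measurement; the documents do not show that intent. Sites must still follow the sentence as it stands, so a slip also needs correcting.
- Criterion 4 does not say who decides that FFR is needed, or for what purpose. Clinical need is the plain reading, but it is a reading.
- Criterion 5 admits stenoses of 30% to 70%, while the Chinese guideline cited in Section 4 recommends FFR at 50% to 90%. Lesions from 30% to below 50% lie outside that recommendation, so the loss to care is not uniform.

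A reader might also infer that the physician has no way at all to act. Sections 7.1.5 (3) and 14.1 show that this goes too far.

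**Conclusion.** The concern holds in limited form. As written, 7.1.4 excludes the approved control wire's FFR from stent decisions, which conflicts with inclusion criterion 4 and with the protocol's own account of what FFR is for. The rule applies to all 300 planned subjects, with about 100 expected at or below 0.80 and about 200 above, taking the plan's 1:2 ratio as given.

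Two stronger readings are not supported. One is that 100, or 300, subjects would be treated wrongly: no number of changed decisions follows from the documents. The other is that the rule damages the trial's statistical result: the endpoint is settled by the recorded readings and does not depend on later treatment.

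The conclusion assumes that criterion 4 means clinical need and that sites apply the sentence literally. The change is a cheap improvement, not a correction on which the analysis depends.

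**What to change.** Replace the sentence in 7.1.4 with:

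> The FFR from the investigational device must not be used as a basis for stent therapy. The FFR from the control device may be used by the treating physician, but only after the readings of both devices have been recorded for every target vessel of the subject. The first valid recorded reading of each device is the one used in the analysis; any later repeat made for clinical reasons (for example, doubtful hyperemia or drift beyond ±3 mmHg) is documented and does not replace it unless the first reading was a technical failure identified without regard to the other device's value.

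This fits the present order, since the control wire is already used second. The ±3 mmHg limit is the existing pullback check in step 15 of the control-device directions, and the repeat clause leaves room for the hyperemia caution in the investigational-device directions. A repeat needed for care is allowed; it simply does not enter the analysis.

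**Cost.** The revision needs agreement between the sponsor and the site investigators (Section 14.2) and written ethics committee approval (Section 12.2). If the consent form describes how the readings are used, it would need matching changes under Section 12.3; the form was not available to check. Some operator stake in the control reading remains. The endpoint definition, the sample size of 300 and the planned analysis stay as they are.
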